12.8. Handling of Dropouts and Missing Data

Every effort will be made to collect all data at specified times. All subjects and data will be assessed up to the time that the subject is dropped. Missing data will be noted in the CRFs.

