7.7. Subject Discontinuation or Withdrawal

Subjects should be encouraged to complete all study outcome assessments. However, a subject may be discontinued from study drug or may withdraw assent/consent to participate in this study at any time without penalty or loss of benefits to which the subject is otherwise entitled. Subjects will be assessed for safety of ceftaroline at the time points outlined in the schedule of evaluations, if possible.

7.7.1. Off Study Criteria:

- Subjects who require continued home parenteral antibiotics will be discontinued from the study.
- Subjects that require IV treatment after switching to Oral drug.
- If a subject's estimated CrCl decreases to < 50 mL/min during the treatment period, the subject will be discontinued from the study.
- Diarrhea (the occurrence of > 4 loose stools /day) with blood or mucus
- Moderate to severe maculopapular rash that does not resolve following administration of diphenhydramine (Benadryl®) or any urticarial rash.
- Absolute neutrophil count < 500 WBC/mm³ (Grade 4)
- Hemolytic anemia Grade 2 (evidence of > 2 g decrease in hemoglobin but does not require blood transfusion) or above.
- Thrombocytopenia-Platelet count < 100,000/mm³ (Grade 1)
- AST/ALT > 3 X ULN (grade 3)

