7.8. Premature Discontinuation From Study Drug Administration

7.8.1. Discontinuations Due to Safety

Assessments and Procedures: A subject who is prematurely discontinued from study drug administration (ie, before the anticipated full course of study drug required for effective treatment of hematogenous SA osteomyelitis *for safety reasons*) should have EOIV or EOT (if on PO drug) assessments conducted per Section 9, and undergo subsequent assessments at FU, if possible. The same procedures will be followed if the subject needs to continue home IV therapy to complete treatment because the subject is intolerant of an appropriate oral antibiotic or there is no oral agent that is active against the organism isolated.

Clinical Outcome Assessment:

If a subject prematurely discontinues the study drug due to an SAE and requires alternative non-study antimicrobials for hematogenous SA osteomyelitis, the subject should be assessed indeterminate.

Reasons: Reason(s) for premature discontinuation from study drug administration *due to safety* may include, but are not limited to, the following:

- Occurrence of an SAE that, in the opinion of the Investigator, warrants the subject's permanent discontinuation from the study drug or oral drug administration.
- Known pregnancy or breastfeeding during the drug administration period. A female subject whose pregnancy test is positive at the end of total treatment must be followed through the immediate postnatal period or until termination of the pregnancy. Every pregnancy will be reported as soon as possible (within 24 hours of learning of the pregnancy), as described in Section 11.1.4.

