7.8.2. Discontinuations Due to Insufficient Therapeutic Effect

Assessments and Procedures: A subject who is prematurely discontinued from study drug administration *due to insufficient therapeutic effect* should have EOIV (if on IV study drug) or EOT (if on PO drug) assessments conducted per Section 9, and undergo subsequent safety assessments at the 4 to 6 week follow up visit. If a subject is discontinued from IV study drug administration *due to insufficient therapeutic effect* and is switched to an alternative IV antibiotic, the alternative therapy should be recorded.

Clinical Outcome Assessment: A subject who is prematurely discontinued from study drug administration *due to insufficient therapeutic effect* should be assessed as a clinical failure on the day of discontinuation. Such a subject will be automatically assigned an outcome of clinical failure at all subsequent evaluation time points.

Reasons: Reason(s) for discontinuation from study drug administration *due to insufficient therapeutic effect* may include, but are not limited to, the following:

- Clinical Worsening: A subject who shows signs of clinical worsening may be prematurely discontinued from study drug administration at any time. If the Investigator deems the benefit-to-risk ratio of continuing study drug acceptable, study drug administration for at least 48 hours is encouraged before discontinuation. If the subject is improving clinically but the blood cultures are persistently positive for *S. aureus* for up to 5 days, ceftaroline can be continued at the discretion of the investigator.
- Lack of Clinical Progress: For a subject who is stable, yet does not show signs of improvement, the Investigator is encouraged to continue study drug administration at least 48 hours before such a subject is assessed as a clinical failure and the subject is prematurely discontinued from study drug.

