7.8.3. Withdrawal

Assessments and Procedures: A subject may withdraw from the study, or be withdrawn at the request of their parent(s) or legally acceptable representative(s), the Investigator, or Sponsor. A subject who is withdrawn completely from this study during study treatment should be encouraged to undergo, if possible, EOIV (if on IV study drug) or EOT (if not on IV study drug) assessments per Section 10, respectively, on the day of withdrawal.

Clinical Outcome Assessment: A subject withdrawn from the study who is not assessed as a clinical failure should be assessed as indeterminate at all subsequent outcome evaluation time points.

Reasons: Reason(s) for withdrawal from the study may include, but are not limited to, the following:

- Withdrawal of assent or consent
- Lost to follow up
- Significant subject noncompliance, defined as refusal or inability to adhere to the prescribed dosing or

- follow-up regimen
- Investigator determination that it is in the best interest of the subject to withdraw from the study, due to reasons other than an SAE.

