8.4. Criteria for Switching to Oral Drug

A switch to PO drug (see Section 9.2.2) is allowed on or after EOIV assessments are completed and if all of the following criteria are met:

- Received at least 48 hours of IV study drug.

- Clinical signs and symptoms have been assessed.
- Ability to maintain oral intake.
- Afebrile (temperature $\leq 38.0^{\circ}\text{C}$) for at least 48 hours.
- Blood cultures are negative for 48 hours.
- CRP decreased compared with baseline value.
- Absence of new or improvement in at least 1 of the following signs and symptoms and worsening of none:
 - Extremity movement or pain.
 - Able to ambulate either unaided or with a walker or crutches.

Subjects that require IV treatment after switching to Oral drug will be discontinued from the study.

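### Do exits for home IV or renewed IV treatment, with no stated efficacy denominator, bias end-of-therapy and one-year success upward?

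*Combined protocol and SAP*

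**What the plan says.** Two off-study rules matter here. Section 7.7.1 states "Subjects who require continued home parenteral antibiotics will be discontinued from the study", and Section 8.4 states "Subjects that require IV treatment after switching to Oral drug will be discontinued from the study". Section 12.8, the only text on missing data, says "All subjects and data will be assessed up to the time that the subject is dropped" and adds that gaps are noted on the case report forms.

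The outcome rules are in Section 7.8:

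- **7.8.2, insufficient therapeutic effect:** the child is a clinical failure on the day of discontinuation, and "Such a subject will be automatically assigned an outcome of clinical failure at all subsequent evaluation time points".
- **7.8.3, withdrawal:** "A subject withdrawn from the study who is not assessed as a clinical failure should be assessed as indeterminate", again at all later time points.
- **7.8.1, safety:** for a child who stops study drug because of an SAE, the rule reads "requires alternative non-study antimicrobials for hematogenous SA osteomyelitis, the subject should be assessed indeterminate".

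On follow-up after an exit, Section 7.7 says "Subjects should be encouraged to complete all study outcome assessments". Section 7.8.1, having set out end-of-IV or EOT visits and later follow-up where possible, adds "The same procedures will be followed if the subject needs to continue home IV therapy to complete treatment" for children with oral intolerance or no active oral agent. Section 4.5 mentions outcome at discharge and safety at the end of ceftaroline.

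Section 12.1 defines the safety population as everyone dosed. Sections 12.3 and 12.5 list the efficacy outcomes without a population and without saying how indeterminate children count.

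**The concern.** A child who goes back to IV treatment because the infection is not controlled has, in substance, a poor outcome. The text that removes such a child does not point to an outcome category. Because the child is then off study, the case could be read either as a failure (7.8.2) or as a withdrawal that is indeterminate (7.8.3). If it were called indeterminate and indeterminates were left out, the success proportion would be computed among children selected for doing well. In a single-arm, open-label trial of 18 children there is no comparator to offset that, and each child is worth 1/18 = 5.6 percentage points. The follow-up wording in 4.5, 7.7, 7.8.1 and 12.8 also differs, so the one-year result might be missing for these same children.

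**Working it through.** **1. The plan's own figure.** Section 6.2 gives N = 18 from A'Hern's single-stage design with null 0.50, alternative 0.80, type 1 error 0.05 and power 80%. Taking success as at least 13 of 18:

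- P(X ≥ 13 | 18, 0.50) = (8568 + 3060 + 816 + 153 + 18 + 1)/2^18 = 12616/262144 = 0.0481.
- P(X ≥ 13 | 18, 0.80) = 0.867.

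No smaller n meets both limits, so 18 is reproduced. Section 6.2 does not name the endpoint behind this proportion, and Section 12 plans no test of EOT or one-year outcome. The denominator question therefore changes neither N nor a stated test.

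**2. Which rule reaches which exit.**

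| Exit | Text that applies | Category on a natural reading |
|---|---|---|
| Return to IV for the infection after the oral switch | 7.8.2 provides for EOT assessments in a child on oral drug. 8.4.1 calls the oral agents study drugs. 10.3 treats worsening from lack of effect of any study drug as an efficacy endpoint. | Failure, carried forward |
| Home IV because response is inadequate | 7.8.2 | Failure, carried forward |
| Home IV for oral intolerance or no active oral agent | 7.8.1 for visits. 7.8.3 as the remaining default, since its list of reasons is open-ended. | Indeterminate unless already a failure |
| SAE needing other antimicrobials | 7.8.1 | Indeterminate |

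What is missing is a cross-reference from 7.7.1 and 8.4 to these rules. The outcome rules themselves are there.

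**3. Size if the rule were passed over.** The documents give no exit rate, so the number of children r returning to IV for the infection is assumed to be 1 or 2, with all others successes. Exact limits for x successes in n are the 0.025 quantile of Beta(x, n − x + 1) and the 0.975 quantile of Beta(x + 1, n − x). When x = n the lower limit is 0.025^(1/n).

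| r | Failure under 7.8.2 | Left out | Difference |
|---|---|---|---|
| 1 | 17/18 = 94.4% (72.7 to 99.9) | 17/17 = 100% (80.5 to 100) | 5.6 points |
| 2 | 16/18 = 88.9% (65.3 to 98.6) | 16/16 = 100% (79.4 to 100) | 11.1 points |

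The second row is less reachable than it looks. Section 7.10 stops the study at two treatment failures, so if these children count there, 16/18 requires the second failure to fall after enrolment is complete.

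**4. Size of the denominator choice alone.** Assume 1 failure and k indeterminates from any cause, so that successes = 17 − k.

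| k | Evaluable only | Indeterminate as non-success | Indeterminate as success |
|---|---|---|---|
| 1 | 16/17 = 94.1% | 16/18 = 88.9% | 17/18 = 94.4% |
| 2 | 15/16 = 93.8% | 15/18 = 83.3% | 17/18 = 94.4% |
| 3 | 14/15 = 93.3% | 14/18 = 77.8% | 17/18 = 94.4% |

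The spread shows how much any convention matters with 18 children. It does not measure upward bias: the low column arises only by scoring children of unknown outcome as non-successes, and the evaluable-only figures lie between the other two.

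**The case for a change.** The strongest point on the other side is that, even with every exit classified, no sentence says whether an indeterminate child stays in the denominator. That is true. With three indeterminates and one failure the same data can be shown as 14/15 = 93.3% (68.1 to 99.8) or 14/18 = 77.8% (52.4 to 93.6), and the choice could be made after outcomes are known. It is also true that 7.7.1 says discontinued where 7.8.3 says withdrawn, and that 12.8 sits awkwardly beside the follow-up encouraged in 7.7 and 7.8.1.

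Two things limit the force of this. First, failure under 7.8.2 is assigned on the day of discontinuation, before any analysis, so the children whose exit most clearly reflects poor response are already fixed as failures. Second, the obvious stricter rule, counting every unobserved exit as a non-success, is not clearly better. It overrides the neutral category that 7.8.1 and 7.8.3 assign, and it would understate success for a child who left because of oral intolerance. In 18 children, counts of success, failure and indeterminate let a reader form either proportion.

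The follow-up wording is partly compatible: 4.5 can be read as a minimum, with 7.7 and 7.8.1 asking for more where possible. The remaining tension with 12.8 is one of wording. Whether a renewed-IV child counts toward the stop in 7.10 is a separate matter for the sponsor.

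**Conclusion.** The concern does not call for a change. Read together, 7.8.2 and 7.8.3 give each exit an outcome category. An upward bias in EOT or one-year success needs two steps that the plan does not direct: passing over 7.8.2 for a child whose infection required renewed IV, and then excluding indeterminates. If both were taken, one such child would move the estimate by 5.6 points, with widely overlapping exact intervals (72.7 to 99.9 against 80.5 to 100).

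This rests on assumed exit counts and on the natural reading that renewed IV for the infection is insufficient effect. Inclusion criterion 4 selects children expected to move to oral therapy before discharge, which should keep home-IV exits few. The outcomes concerned are secondary and descriptive, with no stated test. The primary safety analysis has its own defined population, N = 18 stands, and the end-of-IV response is assessed before oral drug starts, so a later return to IV cannot alter it. What remains is an unstated denominator and a missing cross-reference, which an analyst would fill sensibly by reporting the counts in each category.

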13. ADMINISTRATIVE ASPECTS

13.1. Compliance with Regulatory Requirements

This study will be conducted in compliance with the current ICH E6 GCP, the ethical principles of the Declaration of Helsinki, current FDA GCP guidelines, and any additional national or IRB -required procedures, whichever represents the greater protection for the individual.

13.2. Institutional Review Board

The IRB must approve the protocol or amended protocol (if applicable) and the corresponding ICF (and assent form, if applicable) before the study may be initiated and/or amendments are instituted (unless required for subject safety); and any recruiting materials before use.

The Investigator is responsible for informing the IRB of any changes made to the protocol, and to advise the IRB, at least once a year, about the progress of the study. The Investigator is also responsible for notifying the IRB of any significant AEs that occur during the study according to local IRB requirements.

13.3. Informed Consent

This study will be conducted in compliance with current ICH E6 GCP pertaining to informed consent, the current CFR (Title 21, Parts 50 Subparts B and D, 56 and 312). For a child to participate in the study, the child's parent(s) or legally authorized representative(s) will sign and date the ICF at the first visit, after having been informed about the nature and purpose of the study, participation and termination conditions, risks, and benefits, before initiation of any study-related procedures. A pediatric subject who is _____ old enough to provide assent, will be asked for such assent, according to institution-specific guidelines. A copy of the signed ICF (and assent form, if applicable), must be provided to the subject's parent(s) or legally acceptable representative(s). If applicable, the ICF (and assent form, if applicable) will be provided in certified translation for non-English-speaking subjects and parents or other legally acceptable representatives. Signed ICFs (and assent form, if applicable) will remain in the subjects' study files and be available for verification at any time.

13.4. Confidentiality

Personal study patient data collected and processed for the purposes of this study will be managed by the investigator and his/her staff with adequate precautions to ensure the confidentiality of those data, and in accordance with applicable national and/or local laws and regulations on personal data protection.

Monitors, auditors and other authorized agents of Cempra Pharmaceuticals, the IRB approving this research, and the FDA, as well as any other applicable regulatory authorities, will be granted direct access to the study subjects' original medical records for verification of clinical trial procedures and/or data, without violating the confidentiality of the patients, to the extent permitted by the law and regulations. In any presentation of the results of this study at meetings or in publications, the patient identities will remain confidential.

13.5. Compensation, Insurance, and Indemnity

Information regarding compensation, insurance, and indemnity is presented in the clinical trial research agreement.

13.6. Protocol Amendments

If a protocol has been filed with regulatory agencies or submitted to an IRB and requires changes, a protocol amendment will be written. Any changes to the protocol will be made by the Investigator. Changes to the protocol will be submitted to regulatory agencies when required.

13.7. Case Report Forms

be used for this trial. Study specific electronic case report forms (eCRFs) designed to provide reliable and secure data entry for clinical research purposes will be utilized. The web based software tools in the CTMS employ 2048-bit Secure Socket Layer (SSL) encryption; all transactions are encrypted in both directions. The CTMS meets the regulatory requirements of HIPAA and 21 CFR Part 11 compliance. In addition, the system has an offsite, fully mirrored disaster recovery backup.

Data entered into the CTMS will include a subject identifiers and study identification number; the subject identifiers other than the study identification will not be included in the database reports when required. All data changes in the CTMS are written to an audit trail that identifies the user, date and time, as well as the old value and new value. Both patient-related data as well as trial configuration data are written to the audit trail. Data are saved at regular intervals during data entry to prevent loss of information in the event of a disruption of the Internet connection.

The eCRFs include standard logical checks and range checks, as well as support for multiple languages in the user interface. There is emphasis on tracking deadlines and milestones with automated notifications and reports of study progress. The module includes a data locking mechanism to ensure that data accuracy and integrity are maintained to facilitate data analyses promptly after study completion. Several levels of security are employed to ensure privacy and integrity of the study data, including the following:

- Study access requires use of assigned unique user names and passwords that are modified at specified time intervals
- Individual roles and access levels are assigned
- Passwords are changed regularly
- Data are not stored on laptop computers

The study coordinator will be responsible for data entry and maintaining appropriate source documentation. Source documentation refers to original records of observations, clinical findings and evaluations that are subsequently recorded as data.

The study coordinator will enter data within 7 days of the screening visit and within 14 days of each subsequent visit.

13.8. Source Document Maintenance

Source documents may include, but are not limited to, study progress notes, study- or subject-specific e-mail correspondence, computer printouts, laboratory data, and recorded data from automated instruments. The original signed ICF (and assent form, if applicable) for each participating subject shall be filed with records kept by the Investigator. All documents produced in this study will be maintained by the Investigator and made available for inspections.

13.9. Study Monitoring/Quality Assurance

The study data will be reviewed by the Investigator and the QA Analyst as per the internal institutional SOPs.

The Investigator will allow the applicable regulatory authorities to inspect facilities and records relevant to this study.

13.10. Study File Management

The study file will contain all required documents as per the regulations, IRB requirements and the internal SOPs including, but not be limited to:

- Final study protocol.
- Protocol amendments (if applicable).
- Study manual (if applicable).
- ICF and assent (blank).
- Revised ICFs and/or all addenda (blank).
- Copy of signed form(s) Form FDA 1572.
- Curricula vitae of investigator and sub investigators.
- Documentation of IRB approval of protocol, consent form, any protocol amendments, and any consent form revisions.
- Annual IRB updates and approvals.
- All correspondence between the investigator, IRB, Allergan and FDA.
- Copies of all IND safety reports submitted to the FDA and IRB correspondence documenting their submission (if applicable).
- Laboratory certifications/normal laboratory value ranges.
- Screening log.
- Study drug accountability records and invoices for receipt/return of study drug.
- Protocol signature page.
- Laboratory director's curriculum vitae and medical/professional license, if available.

13.11. Study Completion

The following data and materials will be on file before a study can be considered completed or terminated:

- Laboratory findings, clinical data, and all special test results from screening through the end of the study follow-up period.
- eCRFs properly completed by appropriate study personnel and electronically signed and dated by the investigator.
- Complete drug accountability records (drug inventory log and an inventory of returned or destroyed clinical material).
- Copies of protocol amendments and IRB approval/notification, if appropriate.
- A summary of the study prepared by the principal investigator (an IRB summary letter is acceptable).

13.12. Audits

During the course of the study, or after completion of the study, FDA and/or other regulatory authorities may audit the study. Every attempt will be made to notify Allergan in writing in advance of the audit.

13.13. Retention of Records

It is the responsibility of the Investigator to ensure that the essential documents are available in the Investigator's files or at the institutional center. Any or all of these documents should be available for monitoring and inspection by the regulatory authorities as defined in the monitoring plan.

Records and documents pertaining to the conduct of this study in all formats (including, but not limited to, written, electronic, magnetic, and x-rays) must be retained by the Investigator for at least 15 years after study completion unless local regulations or institutional policies require a longer retention period. These records include eCRFs, source documents, ICFs (and assent form, if applicable), regulatory documents, clinical reports and laboratory results (including, but not limited to, all local and central laboratory results),

After the required retention period, long-term storage arrangements will be made for such study records if possible.

If the Investigator for the study retires, relocates, or for other reasons withdraws from the responsibility of keeping study records, custody must be transferred to a suitable alternate custodian employee of the institution or to a suitably qualified and responsible third party.

At the request of a subject's parent(s) (or other legally authorized representative[s]), medical information may be given to the subject's personal physician or other appropriate medical personnel responsible for the subject's welfare.

